#### 14.9 Unscheduled Visits

Unscheduled visits may be necessary due to AEs or other reasons. The Investigator may examine a patient as often as is medically necessary while the patient is enrolled in the study. Any follow-up that is performed to monitor patient safety should be recorded as an Unscheduled Visit.

#### 14.10 Patient Withdrawal from Treatment or Study

#### **14.10.1 Handling of Withdrawals**

Patients (or their legally authorized representative) may choose to withdraw from the study for any reason at any time without prejudice. The study assessments for the Early Termination Visit should be conducted in the event a patient discontinues from the study prematurely. If a patient withdraws from the study, he or she may not reenter the study.

The Principal Investigator or the Sponsor may withdraw a patient from the study for any of the following reasons:

- Adverse event
- Prohibited therapy (patient requires concomitant medication or a medical procedure prohibited by the protocol)
- Subject noncompliance (patient does not adhere to the requirements specified by the protocol)
- Subject improper entry (patient was enrolled in the study but did not meet the eligibility criteria)
- Subject withdrawal of consent
- Pregnancy (patient becomes pregnant)
- Lost to follow-up
- Death

At the time of withdrawal, the Principal Investigator should advise the patient of the other available options. When a patient is withdrawn from the study for any reason, the reason(s) for withdrawal will be recorded in the eCRF. For any patient who withdraws due to an AE, the reason for withdrawal must be recorded as an AE and not any other reason. Whenever possible, all patients who withdraw from the study prematurely will undergo assessments listed for the Early Termination visit.

If a patient fails to return for a scheduled visit, it is the responsibility of the Principal Investigator or designee to document all efforts to contact the patient and to determine the reason the patient did not return. If a patient cannot be contacted with 3 documented telephone call attempts,

followed by a certified letter, and does not have a known reason for discontinuation (e.g., withdrawal of consent or an AE), the reason for discontinuation will be recorded as "lost to follow-up". The date that the certified letter was mailed will be considered the date of study withdrawal.

In the event of a patient death during the study, the date of death (as listed on the death certificate) will be used as the date of study withdrawal.

It is vital to obtain follow-up data on any patient who is withdrawn due to an AE. In such cases, every effort must be made to undertake protocol-specified safety follow-up procedures.

The Medical Monitor should be notified promptly when a patient is withdrawn.

The Sponsor may terminate the study at any time for clinical or administrative reasons and may discontinue participation by an individual Investigator or site for poor enrollment or noncompliance.

#### 14.10.2 Replacements

Patients who discontinue from the study prior to the pre-procedure safety evaluation following their last injection may be replaced.

#### 14.10.3 Sponsor or Regulatory Agency Termination of the Study

Although the Sponsor intends to complete the study, the right is reserved to discontinue the study at any time for clinical or administrative reasons, or if required by the local regulatory authority.

# **15 STUDY ASSESSMENTS**

This section describes the study assessment procedures. See Study Flowchart and Assessments (Section 21.1 - Appendix A) for timing of each assessment.

## 15.1 Informed Consent

Each site will be required to obtain IRB/EC approval of the ICF. Before any study specific procedures are performed, the investigator or designee will provide the subject or the subject's legally authorized representative with a copy of the current IRB/EC approved ICF and allow adequate time for review and the opportunity to ask any questions regarding the study and/or ICF. The Investigator should answer all questions to the best of his ability and to the satisfaction of the subject or the subject's legally authorized representative before performing any study visit assessments. The ICF should be signed and dated by the subject or subject's legally authorized representative, the Investigator or his designee, and witness (where applicable) before any study specific procedures are performed.

The consenting process must be conducted in accordance with ICH GCP and local regulatory and/or IRB/EC requirements. A copy of the signed and dated ICF should be given to the subject or the subject's legally authorized representative and a copy should be maintained in the subject's medical records. The consenting process should be documented in the subject's source record including the names of persons participating in the discussions and a brief summary of what was discussed including questions and responses.

If the protocol is amended or new safety information becomes available, and revisions are required to the ICF, the subject or subject's legally authorized representative will be required to sign the updated IRB/EC approved ICF.

If a subject or subject's legally authorized representative withdraws consent at any time the date and time and details of the discussion should be recorded in the subject's source record along with the names of the persons participating in the discussion.

## 15.2 Eligibility Assessment

The Investigator must contact the study Medical Monitor when a potential patient is identified for the study to ensure there is space in the cohort. Screening assessments will be used to determine eligibility before enrolling a patient in the study cohort.

## **15.3 Demographic Data**

Demographic data will be recorded including date of birth, gender, race and ethnicity.

## 15.4 Medical, Surgical, and Ocular History

Medical history will be recorded and should elicit all major illnesses, diagnoses, and surgeries for the patient. Ocular history will also be recorded and should be specific to which eye as appropriate.

## **15.5 Prior and Concomitant Therapy**

Prior and Concomitant Therapy taken from 30 days prior to Screening through the last study visit will be recorded. The patient's source record should include start and stop dates, dose, route, frequency, and indication.

## 15.6 Vital Signs

Vital signs should be taken when the patient is adequately rested (after the patient has been resting in a seated position for at least 5 minutes). Vital signs measurements include blood pressure (systolic and diastolic in millimeter of mercury (mmHg)), heart rate (beats/minute), respiratory rate (breaths/minute), and temperature (°C).

#### **15.7** Abbreviated Physical Examination

Abbreviated physical examination should include at a minimum assessments of general appearance, cardiovascular, respiratory, neck/HEENT (head, eyes, ears, nose and throat), and dermatologic. Height and weight will be measured at Screening only. Additional assessments should be completed at the judgment of the Investigator.

#### **15.8 Best-corrected Visual Acuity**

Best-corrected visual acuity (BCVA) will be measured for each eye, pre-treatment prior to dilating eyes, using standard Early Treatment Diabetic Retinopathy Study (ETDRS)-like retroilluminated charts. BCVA will be recorded as the total letter score in each eye.

Visual acuity testing will be performed by qualified site personnel, and should occur before any examination requiring contact with the eye. In order to provide standardization and well-controlled measurements of BCVA during the study, all measurements at a single site must be consistently done using the same lighting conditions, correction, chart type, and measurement procedure for an individual patient throughout the study.

A study specific refraction and BCVA testing protocol will be provided in a separate BCVA testing and imaging procedures manual.

#### **15.9** Slit-lamp Biomicroscopy

Slit-lamp biomicroscopy will be performed for each eye by qualified site personnel. Slit-lamp biomicroscopy, including magnification, will be performed without dilation of the pupil and consistent with standard clinical practice. The patient will be seated during the examination. This procedure should be conducted in the same manner for all patients and will include an assessment of each of the following as normal or abnormal:

- Eyelids
- Conjunctiva
- Cornea
- Anterior chamber

- Iris
- Lens

All abnormal findings that are clinically significant will be described. A change from normal to abnormal for any biomicroscopic variable will be considered clinically significant.

## **15.10 Intraocular Pressure**

At each study visit IOP will be measured according to routine clinical practice using contact tonometry (e.g. Goldmann Applanation, Tono-Pen). It is recommended that the same instrument be used throughout the duration of the study for each patient. At injection visits, IOP will be measured in both eyes before the injection by qualified site personnel, and in the study eye only after intravitreal injection (in Cohort 3, IOP will be measured in the study eye following each of the two injections). Measurements will be recorded in mmHg (e.g., 19 mmHg). At the 1 day post-treatment visits, a single IOP measurement will be performed in the study eye only. At other study visits IOP will be measured in both eyes by qualified site personnel. Elevated IOP should be clinically managed in accordance with routine clinical care of the practice and in accordance with investigator judgment.

The tonometer must be calibrated for accuracy before the first patient in the study at a given site undergoes the first examination, and continue to be performed in accordance with the manufacturer's specifications until the last patient at the site has exited the study.

## 15.11 Dilated Ophthalmoscopy

A dilated fundus examination of the study eye will be performed pre-treatment in all patients by designated qualified site personnel. The following will be observed for the presence of abnormalities:

- Vitreous body
- Peripheral Retina
- Macula
- Choroid
- Optic nerve

All abnormal findings that are clinically significant will be described. A change from normal to abnormal for any ophthalmoscopic variable will be considered clinically significant.

## **15.12** Color Fundus Photography

Color fundus photography (CFP) for each eye will be performed to assess the retina and characteristics of the ocular tumor in the study eye. Color fundus photographs will be obtained using a digital fundus camera and will be performed by designated qualified site personnel.

For detailed instructions regarding performance of CFP, please refer to the BCVA testing and imaging procedures manual provided separately.

## 15.13 Ophthalmic Ultrasound

Ophthalmic ultrasound of the study eye will be performed to assess and measure (depth, width, and height) the ocular tumor from the external surface of the sclera. Ophthalmic ultrasound will be performed by designated qualified site personnel.

For detailed instructions regarding collection of ultrasound measurements, please refer to the BCVA testing and imaging procedures manual provided separately.

## 15.14 Spectral-Domain Optical Coherence Tomography

Spectral-domain optical coherence tomography (sdOCT) imaging of the study eye will be performed to measure and assess cross-sectional images of the anatomic layers of the retina, the ocular tumor and associated pathological changes. sdOCT will be performed pre-treatment during visits in which ICON-1 is administered. sdOCT imaging will be obtained using a Spectral-Domain (High Definition) OCT device by designated qualified site personnel. Preferably the same machine will be used for initial and follow-up assessments of each patient.

For detailed instructions regarding collection of sdOCT imaging, please refer to the BCVA testing and imaging procedures manual provided separately.

#### 15.15 Enhanced Depth Imaging Optical Coherence Tomography

Enhanced depth optical coherence tomography (EDI-OCT) imaging of the study eye will be performed optionally, according to investigator judgment, to evaluate the structural changes of the choroid in the area of the tumor.

EDI-OCT will be performed pre-treatment during visits in which ICON-1 is administered. EDI-OCT imaging will be obtained using an EDI-OCT device by designated qualified site personnel. Preferably the same machine will be used for initial and follow-up assessments of each patient.

For detailed instructions regarding collection of EDI-OCT imaging, please refer to the BCVA testing and imaging procedures manual provided separately.

## 15.16 Fluorescein Angiography

Fluorescein angiography (FA) imaging (after intravenous administration of Fluorescein dye) for each eye will be performed to examine the circulation of the retina and characteristics of the ocular tumor in study eye according to standard FA image capture protocol. FA images will be obtained using a digital camera by designated qualified site personnel.

For detailed instructions regarding collection of FA images, please refer to the BCVA testing and imaging procedures manual provided separately.

## **15.17 ICG Angiography**

Indocyanine green angiography (ICGA) imaging (after intravenous administration of Indocyanine Green dye) for each eye will be performed optionally, according to investigator judgment, to examine the blood vessels and connective tissue of the choroid and the ocular tumor in the study eye. ICGA images will be obtained using an infra-red sensitive camera by designated qualified site personnel.

For detailed instructions regarding collection ICG imaging, please refer to the BCVA testing and imaging procedures manual provided separately.

#### 15.18 Clinical Laboratory Evaluations and Immunogenicity

Blood samples for routine clinical laboratory tests and immunogenicity tests will be collected. The minimum tests to be performed include:

- Hematology (complete blood count including white blood cell [WBC] count, WBC differential, red blood cell [RBC] count, hematocrit [Hct], hemoglobin [Hgb], mean corpuscular volume [MCV], mean corpuscular hemoglobin [MCH], mean corpuscular hemoglobin concentration [MCHC], red cell distribution width [RDW], platelet count, mean platelet volume [MPV], and C-reactive protein [CRP])
- Serum chemistry profile (albumin, alkaline phosphatase, alanine aminotransferase [ALT], aspartate aminotransferase [AST], blood urea nitrogen [BUN], calcium, serum chloride, carbon dioxide [CO2], creatinine, BUN/creatinine ratio, creatinine clearance [CrCl] using Cockcroft-Gault formula, creatine phosphokinase [CPK], direct and total bilirubin, triglycerides, gamma-glutamyl transferase [GGT], globulin, glucose, lactic dehydrogenase [LDH], phosphorus, potassium, sodium, total cholesterol, total protein, uric acid)
- Serum pregnancy test for women of child bearing potential
- Coagulation (PT, INR, fibrinogen, and activated partial thromboplastin time [aPTT])
- Immunogenicity (plasma anti-drug antibody [ADA])

Any abnormal test results determined to be clinically significant by the Investigator should be repeated at the discretion of the Investigator until the cause of the abnormality is determined, the value returns to baseline or to within normal limits, or the Investigator determines that the abnormal value is no longer clinically significant. Clinical laboratory results should be initialed and dated by the Investigator and any abnormal results should be marked as clinically significant or not clinically significant. Clinically significant laboratory results should be recorded as an AE, preferably as a diagnosis where possible.

Blood samples will be obtained to measure systemic levels of anti-drug antibodies. Blood samples for measurement of anti-drug antibodies will be drawn before the first intravitreal injection at Screening/Baseline before the intravitreal injection and at Week 2, Week 8 and the Early Termination visit (as applicable).

Female patients with a positive pregnancy test at Screening do not meet the eligibility criteria and may not enroll in the study. Women must have been in menopause for at least 2 years, or had a tubal ligation at least 1 year prior to Screening, or have had a total hysterectomy to be considered **not** of child bearing potential.

It is the investigator's responsibility to perform clinical laboratory assessments more frequently if clinically indicated.

Hematology, serum chemistry, coagulation, and serum pregnancy tests will be performed by a central laboratory. ADA samples will be batch analyzed by a central bioanalytical laboratory. For detailed instructions regarding collection, storage and handling of clinical laboratory and immunogenicity samples, please refer to the Laboratory Manual provided separately.

## 15.19 Pharmacokinetic and Pharmacodynamic Markers

Blood samples for PK (plasma ICON-1 concentrations) and PD markers (including serum cytokine levels, circulating TF, immunophenotype patterns and CTDNA) analyses will be drawn from all study patients at pre-specified time points prior to and after administration of ICON-1.

For all cohorts, blood samples for PK and PD analysis will be collected on Day 0 pre-injection and 4 hours  $\pm 1$  hour post injection (for cohort 3 prior to the first injection and after the second injection), and on Day 1. For cohorts 2 and 3, blood samples for PK and PD analysis will also be collected on Day 7 prior to the first injection and 4 hours  $\pm 1$  hour post injection (for cohort 3, prior to the first injection and after the second injection), and 1 day post Day 7 treatment. In addition, for all cohorts, a blood sample for PD markers will be collected prior to enucleation or plaque placement, as applicable.

Blood samples for CTDNA will be collected along with the other PD marker samples on Day 0 (all cohorts, pre-injection), Day 7 (cohorts 2 and 3 only, pre-injection), and prior to enucleation or plaque placement (all cohorts).

A PK and PD sample will also be obtained at the Early Termination visit if Day 1 or 1 day post Day 7 treatment PK/PD samples were not collected following injection on Day 0 or Day 7, as applicable.

For detailed instructions regarding collection, storage and handling of PK and PD samples, please refer to the Laboratory Instruction Manual provided separately.

## 15.20 Proteomic Analysis of Vitreous

**For Patients Undergoing Enucleation Only:** Immediately following the enucleation procedure, vitreous humor aspirate will be collected for assessment of ICON-1 levels and proteomic analysis of TF and other cytokines, and will be sent to the central study laboratory.

For detailed instructions regarding collection, storage, and handling of vitreous humor samples, please refer to the Laboratory Instruction Manual provided separately.

## 15.21 Tumor Pathology, Genetic Profiling and Exome Sequencing

**For Patients Undergoing Enucleation:** Following the enucleation procedure, the eye globe will be sent to the local site laboratory for pathology according to the clinical site's standard of care practice. A subset of pathology slides and/or tumor block samples will be prepared by the local laboratory and sent to the study central laboratory for study-related assessments, including ICON-1 binding to TF within the tumor, TF and PAR2 expression, characterization of the immune infiltrate, and alterations of the vasculature, genetic profiling (Type 1 or Type 2), and Exome sequencing. Genetic profiling previously performed with fine needle aspiration of the tumor does not require repeated testing.

A central laboratory designated for the study will perform the above testing for the provided slides and/or tumor block samples. For detailed instructions regarding specimens preparation, handling and shipping, please refer to the Laboratory Instruction Manual provided separately.

**For Patients Undergoing Plaque Placement:** If standard of care fine needle aspiration of the tumor is performed prior to plaque placement for genetic profile testing, the results of that testing will be recorded.

## 15.22 Evaluation of Adverse Events

Adverse events (AEs) will be monitored continuously during the study from the time that the subject has provided written informed consent through the subject's last day of study participation. AEs may be reported spontaneously by the subject, discovered by Investigator or study staff through questioning, or observed through physical examination or other means. It is the responsibility of the Investigator to assess and document all AEs that occur during the course of the study, regardless of the causal relationship with the study drug.

The following information will be collected for all AEs and recorded on the subject's source document and AE eCRF:

- Event description (diagnosis preferred, if unknown, record the signs/symptoms)
- Onset and resolution dates
- Severity (intensity)
- Frequency (intermittency)
- Relationship to study drug (causality) as determined by the Investigator
- Seriousness
- Action taken with study drug
- Corrective action taken
- Outcome

#### 15.22.1 Definition of an Adverse Event

An adverse event (AE) is any untoward medical occurrence in a patient or clinical investigation subject administered a pharmaceutical product and which does not necessarily have a causal relationship with this treatment.

An AE can therefore be:

- Any unfavorable and unintended medical diagnosis, sign or symptom
- Any new undesirable medical occurrence or unfavorable or unintended change in a preexisting condition that occurs during or after study treatment
- Laboratory abnormality, vital sign or ophthalmic assessment that is assessed as clinically significant and different from baseline (e.g., requiring discontinuation of study treatment, specific treatment, or a change in subject management). If possible, changes in laboratory results or changes in vital signs that meet the definition of an AE should be reported as a medical diagnosis rather than as the abnormal value (e.g., "hypertension" rather than "blood pressure increased").

The following are special considerations when determining and reporting AEs:

- Whenever possible, the Investigator should group signs or symptoms that constitute a single diagnosis under a single AE term (e.g., "cough, rhinitis, and sneezing" might be grouped together as "upper respiratory tract infection").
- Pre-existing conditions are not considered AEs unless the condition worsens (increase in frequency, severity or specificity) during or following study drug administration. Fluctuations in a pre-existing condition should be assessed by the Investigator, and those that fall within the limits of expected fluctuations for the disease state, and are not assessed as worsening of the disease, should not be considered AEs. Any change assessed as clinically significant worsening of the disease from baseline must be documented as an AE.
- Elective surgery (including the planned enucleation surgery or brachytherapy, and associated inpatient hospitalization, as applicable) or routine diagnostic procedures are not considered AEs. However, an untoward medical event occurring during the pre-scheduled elective surgery or diagnostic procedure should be recorded as an AE.
- Death itself is not considered an AE; it is instead the outcome of an AE.
- Pregnancy is not considered an AE, but it is an important medical event that must be followed up as described in Section 15.22.8.
- For cohort 3, if the IOP in the study eye following the first intravitreal injection does not stabilize sufficiently to the pre-injection level (i.e., within 5 mmHg of the pre-injection IOP) to perform the second intravitreal injection, the change in IOP should be reported as an AE.
- For cohort 3, elevated IOP in the study eye following the first intravitreal injection should be considered an AE if: (1) two or more follow-up IOP measurements are required to demonstrate stabilization to the pre-injection level (i.e., within 5 mmHg of the pre-injection value), thereby delaying the time of the second intravitreal injection; or (2) interventional therapy is required to return IOP to within 5 mm Hg of the pre-injection value.

A treatment-emergent AE (TEAE) is any AE with an onset from any time after the patient has received study drug through 30 days after the last dose of study drug, whether or not it is considered causally related to the study drug.

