#### 17.6 Safety Analyses

Safety will be assessed through summaries of adverse events, changes in laboratory test results (serum chemistry, hematology, coagulation), and changes in vital signs and physical and ophthalmic examinations. Adverse events will be mapped using MedDRA. Systemic levels of

anti-drug antibodies (ADA) during the study will be collected for each patient. If there are sufficient numbers of patients exhibiting systemic levels of ADA, summary statistics by cohort will also be provided.

All collected adverse event data will be listed by cohort, study site, and patient number. All Adverse Events of Special Interest (AESIs) occurring on or after intravitreal injection will be listed and summarized by cohort. All adverse events occurring on or after treatment on Day 0 (treatment emergent adverse events, TEAEs) will be summarized by cohort. In addition, all serious adverse events, including deaths (if any), will be listed separately. Finally, all ocular adverse events will be listed and tabulated with events for the study and fellow eye summarized separately.

Changes in laboratory data will be summarized by cohort.

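### Section 15.22.1 makes certain IOP rises adverse events by rule in cohort 3 only, and the by-cohort adverse event summaries do not separate them

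*Combined protocol and SAP*

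**What the plan says.** Section 15.22.1 gives a general definition for all cohorts. An adverse event may be a "Laboratory abnormality, vital sign or ophthalmic assessment that is assessed as clinically significant and different from baseline", with discontinuation, specific treatment or changed management as examples.

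The same section then adds two items for cohort 3 alone:

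- The IOP change is to be reported if pressure "does not stabilize sufficiently to the pre-injection level" and the second injection cannot be given.
- "For cohort 3, elevated IOP in the study eye following the first intravitreal injection should be considered an AE if" either of two triggers is met. The first is that "two or more follow-up IOP measurements are required to demonstrate stabilization to the pre-injection level", with the qualifier "thereby delaying the time of the second intravitreal injection". The second is that "interventional therapy is required to return IOP to within 5 mm Hg of the pre-injection value".

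Section 15.10 requires IOP in all cohorts before the injection and "in the study eye only after intravitreal injection", repeated after each injection in cohort 3. It sets neither the time of the post-injection reading nor a recheck interval. The only timing is in section 12.1.2 and Appendix B: the second cohort 3 injection comes at least 30 minutes after the first, once IOP is back within 5 mmHg of its starting value.

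Occurrence of adverse events is a primary endpoint (section 16.1). Section 17.6 states: "All adverse events occurring on or after treatment on Day 0 (treatment emergent adverse events, TEAEs) will be summarized by cohort". It also tabulates ocular events by eye. Nothing there separates events that arise from the cohort 3 rule.

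**The concern.** The rule concerns pressure after the first injection. On Day 0 a cohort 3 patient has at that moment received exactly what a cohort 1 or 2 patient receives: 300 µg in 100 µl. The same short-lived, untreated rise may be an adverse event by rule in cohort 3 and a matter of investigator judgment in the other two cohorts.

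Section 10.3 describes the cohorts as escalating in dose and volume, so readers will look across cohorts for injection tolerability. An excess of IOP events in cohort 3 could come partly from the definition and not from the dose. Since the study has no inferential testing (section 17.1), the descriptive table is the main safety result.

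**Working it through.** **1. Cohort sizes.** Section 12.4 gives planned sizes of 2, 3 and 5 and maxima of 3, 4 and 6. The maxima sum to 3 + 4 + 6 = 13, which reproduces the enrolment figure in section 17.10. The planned total is 2 + 3 + 5 = 10.

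**2. Dosing visits under the rule.** Cohort 3: 5 to 6 patients × 2 visits = 10 to 12. Cohorts 1 and 2: none.

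**3. Where the definitions differ.** The three triggers, compared with the general definition:

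| IOP rise after the first injection | Cohort 3 | Cohorts 1 and 2 |
|---|---|---|
| Needs intervention | AE by rule | Can be an AE; treatment is one of the general examples |
| Prevents the second same-day injection | AE by rule | No such step exists |
| Untreated, settles late, two or more rechecks, second injection delayed | AE by rule | AE only if judged clinically significant |

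The third row carries most of the difference in ascertainment.

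**4. Dependence on site timing.** Assumptions, since the documents give none of these: the settling times and check schedules are illustrative; delay means later than the 30-minute minimum; and a routine reading straight after injection is not counted as a follow-up. Each cell gives the number of follow-up readings needed and the time at which the patient is cleared.

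| IOP settles at | Checks at 15 min, then every 15 | Checks at 30 min, then every 15 | First check at 45 min, then every 15 |
|---|---|---|---|
| 20 min | 2, cleared at 30: no delay, no AE | 1: no AE | 1: no AE |
| 40 min | 3, cleared at 45: AE | 2, cleared at 45: AE | 1, cleared at 45: no AE |
| 50 min | 4, cleared at 60: AE | 3, cleared at 60: AE | 2, cleared at 60: AE |

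The 20-minute row shows that the delay qualifier works: early rechecks alone do not create an event. In the 40-minute row all three sites clear the patient at 45 minutes, yet only the two that looked sooner report an event. The site effect therefore remains, but only for rises that last beyond 30 minutes.

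**5. Weight of one event.** In cohort 3, 1/5 = 20 percentage points, or 1/6 = 16.7 if the cohort is expanded.

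**The case against.** The strongest reply is that the cohort 3 triggers largely apply the general definition to a step that exists only in that cohort. An omitted injection, an intervention and a delayed dose resemble the general examples of discontinuation, specific treatment and changed management. Two of the three triggers do not depend on the number of rechecks. Raw adverse event rates were never like for like, because planned injections per patient are 1, 2 and 4. Section 17.6 already lists every event by cohort, site and patient, so with five or six patients the IOP events can be found by eye. Section 17.1 also leaves further detail to the SAP.

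Most of this stands, and it narrows the point to transient, untreated rises that delay the second injection. It does not remove the point. A listing shows that an IOP event occurred, but not whether it was reported only because of the rule. The summary tables do not separate such events either.

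Three stronger readings are tempting, and the documents do not support them:

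- A reader might infer that any extra recheck creates an event, for instance checks at 10 and 30 minutes against one check at 30. If pressure has settled by 30 minutes the second injection can go ahead at the earliest permitted time, so nothing is delayed and the trigger is not met.
- A reader might infer that IOP events are impossible in cohorts 1 and 2. The general definition still applies there.
- A reader might attach a rate. If a share r of dosing visits met the trigger, the per-patient rate over two independent visits would be 1 − (1 − r)²: 19%, 36% and 51% for r of 10%, 20% and 30%. With complete within-patient correlation it would be only 10%, 20% and 30%. The documents give neither r nor the correlation, so none of these figures is an estimate for this trial.

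**Conclusion.** The point holds in this limited form and is minor. Ascertainment of IOP adverse events differs by cohort by design, mainly for untreated rises that delay the second injection, and one trigger varies with local recheck timing beyond 30 minutes. The rule can only add reported events in cohort 3, but how many cannot be derived from the documents. The 20-point weight of one patient assumes the planned five.

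The effect is confined to IOP events and to the ocular, any-event and TEAE totals that contain them. Systemic events are untouched. Dose-limiting toxicities are inflammation or hemorrhage (section 12.4), so escalation is unaffected. A transient rise of this kind would not by itself be a serious event or an event of special interest. A reader might infer that adverse event rates as a whole cannot be compared across cohorts because of this rule; the documents do not support that.

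**What to change.** Keep the reporting rule as written, and make these changes to data capture and section 17.6:

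1. Add a flag on the adverse event eCRF for events reported only because of the cohort 3 IOP rule.
2. Show the TEAE and ocular adverse event tables by cohort with and without the flagged events.
3. Summarise the change from pre-injection to first post-injection IOP, for the first injection at each dosing visit, in the same way in all three cohorts. List the time of the reading where recorded, because the protocol does not fix it.

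The cost is one eCRF flag and one extra table. No measurement is added, since these readings are already required, and no clinical rule changes. The limitation is that reading times remain unfixed, so the common IOP summary reduces the effect of site timing but does not remove it.
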